# Table 14 - Time Course Distribution of AEs – Post-Crossover HA to APS

2 nd Injection	1 Month	3 Month	6 Month	12 Month

Interval	Injection to Day 15	Day 16 to Day 61	Day 62 to Day 137	Day 138 to Day 274	Day 275 to Day 547
AEs					
AE Type 1					
AE Type 2					
Serious AE					
AE Type 1					
AE Type 2					
Device Related AE					
AE Type 1					
AE Type 2					

A time-course tabulation showing rescue medication use (for index knee OA) by treatment group will also be generated. Adverse Event and Medication Use will be tabulated for all Phase I intervals.

#### 6. Study Populations

A list of protocol violations will be evaluated to determine subjects who (1) violated one or more eligibility criteria, and (2) subjects with major protocol deviations that impact patient safety or the scientific validity of the study comparisons, or have the potential to do so. This will be determined by a blinded review of the protocol deviations.

Results will be tabulated. For the primary endpoint, two analyses will be performed: (1) intent-to-treat (ITT) and (2) per protocol (PP), as defined below. The ITT analysis will be considered the primary analysis of the study, and the PP analysis will be considered as sensitivity analysis.

Secondary endpoints will be analyzed using the per protocol group, with no imputation for missing data. Safety evaluations will be performed on the intent-to-treat group, with no imputation for missing data. Further detail regarding these analysis groups is given below.

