### 1.3 Randomization

Subjects will be randomized to either the APS or HA treatment group on a 1:1 basis. The subjects and investigators will both remain blinded throughout Phase I of the study. Assignment to treatment groups will be stratified by site and will use random block sizes. Specifically, designated unblinded personnel at each site will provide the masked syringe to the injecting health care provider. To protect the double-blind, the treating health care professional and evaluating health care professional will be different individuals. Assignment will not be revealed until after the blood has been drawn for nSTRIDE APS Kit processing.

The randomization plan will be produced using SAS v 9.4 or similar software. Balanced randomization with random block sizes (1:1, APS: HA) will be implemented. In the event that, post-randomization, no study treatment was given, randomization will not be reassigned; however, this case will not count toward the overall sample size. Randomization will continue with the next case enrolled until the minimum sample size is reached in both treatment groups. Randomization will be stratified by site, and each site will receive separate randomization plans using random predetermined block sizes that will remain undisclosed to the sites. The randomization file will be uploaded into the electronic data capture (EDC) system. Once the subject is enrolled into the EDC and has been identified as eligible for randomization, the randomization allocation will be visible within the EDC and viewable only by the unblinded research associate. The subject will be treated according to the contents of the displayed randomization allocation.

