# 5. Safety Endpoints

During Phase I, all Adverse Events will be collected regardless of relationship to the device. During Phase II, only AEs that are potentially related to the device/procedure will be collected.

Adverse events will be designated in MedDRA categories by a qualified reviewer that is blinded with respect to treatment assignment. Specific adverse events are expected to occur at low frequencies, and therefore no significant differences between groups are expected. Accordingly, the *a priori* tests planned will determine whether the overall rate of adverse events differs between treatment groups, and whether differences between groups exist with respect to device relatedness and severity. Results for each category will be tabulated by treatment group. In this tabulation the number of subjects with one or more adverse events fitting into an individual adverse event (AE) category will be displayed beside the count of subjects with no AEs fitting into that category. A Fisher's Exact test will be performed to determine whether treatment groups differ. In addition, the number of AEs and the corresponding percentage of total AEs within each category of severity and relatedness to the device will be summarized by treatment. A listing of all AEs will be provided, and a narrative of each serious AE will be generated.

In addition, a time-course distribution of adverse events will be created based on contiguous intervals between planned visits, as shown in *Table 11*, *Table 12*, *Table 13*, and *Table 14*. In this table, one AE per subject, category, and time interval will be counted.

	Injection	1 Month	3 Month	6 Month	12 Month
Interval	Injection to Day 15	Day 16 to Day 61	Day 62 to Day 137	Day 138 to Day 274	Day 275 to Day 547
AEs					
AE Type 1					
AE Type 2					
Serious AE					
AE Type 1					
AE Type 2					
Device Related AE					
AE Type 1					
AE Type 2					

Table 11. Time Course Distribution of AEs - APS

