#### Intent-to-Treat (ITT)

The ITT population includes all randomized subjects, regardless of whether they received an injection or not. This will be the population used for any data listings, for the primary study analysis, for safety analyses, and for demographic data summarized according to **Table 1**.

A table showing major and minor protocol deviations will be generated, comparing major and minor deviation frequency between the two treatment groups.

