#### Per Protocol (PP)

The PP population includes all subjects from the mITT population who do not have major protocol deviations that impact patient safety or the scientific validity of the study outcomes, or the potential to do so. Analyses which use the PP population will use all available data on these subjects, with no imputation of missing data. This is the population that will be used in the analysis of secondary and exploratory efficacy endpoints, and as a sensitivity analysis of the primary endpoint.

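### Safety is analysed on all randomised subjects, so never-injected subjects count as event-free in injection- and device-related adverse event rates

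*SAP*

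**What the plan says.** The SAP assigns safety to the ITT set in two places. Section 6 (Study Populations) says "Safety evaluations will be performed on the intent-to-treat group, with no imputation for missing data". The ITT definition that follows reads "The ITT population includes all randomized subjects, regardless of whether they received an injection or not", and its list of uses again includes safety: "This will be the population used for any data listings, for the primary study analysis, for safety analyses, and for demographic data".

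Section 1.3 (Randomization) provides for subjects who are randomised and then not treated: "In the event that, post-randomization, no study treatment was given, randomization will not be reassigned". Such cases do not count toward the sample size, and randomisation continues until both groups reach the minimum number.

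Section 5 (Safety Endpoints) sets out the comparison. For each category, the number of subjects with at least one event "will be displayed beside the count of subjects with no AEs fitting into that category", and then "A Fisher's Exact test will be performed to determine whether treatment groups differ". Table 10 adds logistic models by subgroup for any serious adverse event and for any device-related adverse event.

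The only other analysis set is for efficacy: "The PP population includes all subjects from the mITT population who do not have major protocol deviations". The mITT set named there is not defined in the SAP. No treated, safety or as-treated set appears anywhere.

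**The concern.** A rate of injection-related or device-related events should describe people exposed to the injection or the device output. Someone who was never injected cannot have an injection-related event, yet under the ITT rule is added to the event-free column. The SAP itself treats these subjects as not contributing to the trial's size, but it keeps them in the safety denominator.

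Including everyone randomised is the cautious choice for a superiority claim on efficacy. It is not cautious for safety, where it can only lower the rates of exposure-related events.

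Two related gaps follow.

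- Tables 11 and 12 count time from the injection, so a never-injected subject has no day 0 and cannot be placed in them.
- There is no rule for a subject injected with the product that was not assigned. Under an ITT grouping, that subject's events would be reported under the other product.

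**Working it through.** The documents state no adverse event rate, number of uninjected subjects or safety denominator, so there is no planned figure to reproduce. The check is how far the stated rule could move a rate.

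**Inputs**

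- Injected subjects per arm: 123, the planned enrolment per group in SAP Section 6.1. Because Section 1.3 excludes untreated cases from the count, uninjected subjects are taken as additional to the 123.
- Uninjected subjects per arm, u: assumed 0 to 12.
- True rate among injected subjects, r: assumed 20% and 10%.

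**Rate within an arm.** For an event that an uninjected subject cannot have, reported rate = r × 123 / (123 + u). For example, with u = 6: 20% × 123/129 = 19.07%.

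| u per arm | Uninjected share | True 20% shown as | True 10% shown as |
|---|---|---|---|
| 0 | 0% | 20.00% | 10.00% |
| 1 | 0.8% | 19.84% | 9.92% |
| 3 | 2.4% | 19.52% | 9.76% |
| 6 | 4.7% | 19.07% | 9.53% |
| 12 | 8.9% | 18.22% | 9.11% |

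**Difference between arms.** Take true rates of 20% and 10%, and u = 6:

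- in both arms: 10 points × 123/129 = 9.53 points, and the ratio stays at 2.0;
- in the higher-rate arm only: 19.07 − 10.00 = 9.07 points;
- in the lower-rate arm only: 20.00 − 9.53 = 10.47 points.

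The absolute gap can therefore shrink or grow, depending on where the uninjected subjects fall.

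**Power.** For 20% against 10% (normal approximation, two-sided 0.05, equal u in both arms), power is 59.4% with u = 0, 59.3% with 3, 59.1% with 6 and 58.8% with 12. The test is barely affected; the matter is what the reported rate describes.

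**Other product received.** If m subjects per arm received the other product and were counted as randomised, the arms would show (20 × (123 − m) + 10 × m)/123 and (10 × (123 − m) + 20 × m)/123. With m = 6 these are 19.51% and 10.49%, a difference of 9.02 points instead of 10. With m = 1 the difference is 9.84 points, and with m = 3 it is 9.51.

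**The case against.** The strongest reply is that the effect is small, conditional and confined to part of the safety output. Most of that stands.

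- **Not every rate is diluted.** A reader might infer that all adverse event rates scale down by the uninjected share. They do not. Section 5 collects all Phase I events regardless of relationship to the device. The protocol synopsis (Study Design and Procedures) gives every subject a blood draw and records events from it, and SAP Section 1.3 reveals assignment only after that draw. An uninjected subject can have blood-draw, unrelated or serious events. The proportional formula fits injection-related events, and device-related events other than any attributed to the blood draw or kit procedure.
- **The arms are not always pulled together.** Equal dilution leaves the ratio unchanged, and unequal dilution can widen the gap, as shown above.
- **Non-injection is allowed for, not predicted.** Section 1.3 is conditional. Assignment becomes known only after the blood draw at the treatment visit, which leaves little time for dropout between learning the allocation and injection, although the exact moment of randomisation is not stated.
- **Other outputs are untouched.** The percentages of total events by severity and relatedness use events as the denominator. The full listing and the serious-event narratives do not depend on a denominator at all.
- **Wrong-product attribution is an inference.** The SAP does not say outright that safety is grouped as randomised, and it describes no such injection. The inference comes from the use of ITT with no as-treated rule. Planned switching already has its own tables, 13 and 14.

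None of this removes the central point. The rule is stated twice, it puts unexposed people into the event-free count of a planned test, and nothing elsewhere in the SAP corrects it.

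**Conclusion.** The concern holds for subject-level rates of injection-related events, and of device-related events not arising from the blood draw or kit procedure. In the Section 5 Fisher's Exact tables and the device-related row of Table 10, these rates are lowered by the share of the arm that was never injected. On an assumed true rate of 20% with 123 injected per arm, the loss is about 0.5, 0.9 or 1.8 percentage points for 3, 6 or 12 uninjected subjects, and nothing if all are injected. The direction and size of any effect on the between-arm difference depend on how non-injection splits between arms, which the documents do not show. They also do not support reading this as a general understatement of all adverse events or as a bias that always favours one arm.

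The missing as-treated rule is a separate gap of the same kind: it matters only if someone receives the other product, and the documents report no such case. The change is worth making because it is cheap and makes the device-related rates describe exposed subjects, not because a large distortion has been shown.

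**What to change.** Add a safety set to SAP Section 6: all subjects who received a study injection, grouped in Phase I by the product actually received at the first injection. Use it for the subject-level adverse event tests in Section 5, for Tables 11 and 12, and for the safety rows of Table 10. Amend the two statements that now assign safety to ITT.

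State that events after a Phase II crossover are attributed to the product received, in line with Tables 13 and 14. This needs to be explicit because the last interval of Tables 11 and 12 runs to Day 547, past the 12-month visit, and a subject may by then have received both products.

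List adverse events in never-injected subjects, such as blood-draw events, separately so that none is lost. Keep ITT for the primary efficacy analysis. Define the mITT set on which the per-protocol definition relies, or remove the reference.

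The cost is SAP wording and one extra population flag, with no new data. Reported rates of exposure-related events will be slightly higher if any randomised subject was not injected.

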#### Intent-to-Treat (ITT)

The ITT population includes all randomized subjects, regardless of whether they received an injection or not. This will be the population used for any data listings, for the primary study analysis, for safety analyses, and for demographic data summarized according to **Table 1**.

A table showing major and minor protocol deviations will be generated, comparing major and minor deviation frequency between the two treatment groups.

#### Per Protocol (PP)

The PP population includes all subjects from the mITT population who do not have major protocol deviations that impact patient safety or the scientific validity of the study outcomes, or the potential to do so. Analyses which use the PP population will use all available data on these subjects, with no imputation of missing data. This is the population that will be used in the analysis of secondary and exploratory efficacy endpoints, and as a sensitivity analysis of the primary endpoint.

#### 6.1 Sample Size

Data used to estimate sample size are from Zimmer Biomet study APSS-33-00, a randomized study comparing APS to saline in human subjects. This calculation assumes that hyaluronic acid will perform similarly to saline. Estimates of expected difference and pooled standard deviation from this study are shown in **Table 15**.

Group	n	Mean Improvement in WOMAC	St. Dev.	Mean Diff.	Pooled St. Dev.	Sample Size Each	Combined Plus 20% Attrition
		Palli				Group	
APS	30	7.20	3.25				
Saline	15	4.93	4.73	2.27	4.06	93	246

Table 15- Results from APSS-33-00

The calculation results in 93 per group. Results are based on a two-tailed alpha of 0.049 and statistical power of 90%.

Planned enrollment was increased to 123 per group to protect against attrition of approximately 25% in either treatment group.

<sup>1 Under the original sample size calculations, the sample size of 196 randomized (98 per group) was adjusted to accommodate potential dropout rate of approximately 20%, resulting in a total sample size of 246. This sample size

A maximum of 30 sites will participate in the study. Enrollment will be stopped at any site reaching a limit of 30% of planned study enrollment.

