#### $n_{new}=Max(n,n*).$

Therefore, if an increase in sample size is warranted by the re-calculation of the sample size requirements at the interim time point, it will only be reported how many more subjects are required in order to meet the study endpoint at

assumed a 2-sided alpha of 0.025 and power of 0.95. Note that, in accordance with the primary hypothesis, the sample size has been re-calculated under a 2-sided alpha=0.049 (instead of 2-sided alpha = 0.025) and a power of 0.90. This results in a sample size of 93 per group, or 117 when including 20% attrition and 124 when including 25% attrition. Thus the original sample size of 246 is sufficient for testing the primary endpoint with 90% power, and accommodate almost 25% attrition.

sufficient power. The sample size will not be reduced as a result of the sample size re-calculation. The sample size will only be increased, if the reassessment is so indicated. If the reassessment does not indicate an increase in sample size, then the study will continue as originally planned.

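### The stated 93 per group does not follow from Table 15's difference and pooled SD, which give 69; the SAP should name the input behind 93 or correct it, with enrolment of 246 unchanged

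*SAP*

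**What the plan says.** SAP section 6.1 bases the calculation on the sponsor's earlier study of APS against saline: "Estimates of expected difference and pooled standard deviation from this study are shown in" Table 15. That table prints APS n 30, mean 7.20, SD 3.25; saline n 15, mean 4.93, SD 4.73; difference 2.27; pooled SD 4.06; 93 in each group; and 246 as the combined total with 20% attrition. The text then says: "The calculation results in 93 per group. Results are based on a two-tailed alpha of 0.049 and statistical power of 90" per cent. On attrition it adds: "Planned enrollment was increased to 123 per group to protect against attrition of approximately 25% in either treatment group".

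Footnote 1 to section 6.1 gives the history. The original size was "98 per group) was adjusted to accommodate potential dropout rate of approximately 20%, resulting in a total sample size of 246", at two-sided alpha 0.025 and power 0.95. Then "the sample size has been re-calculated under a 2-sided alpha=0.049 (instead of 2-sided alpha = 0.025) and a power of 0.90". The outcome is reported as: "This results in a sample size of 93 per group, or 117 when including 20% attrition and 124 when including 25% attrition". The footnote concludes: "Thus the original sample size of 246 is sufficient for testing the primary endpoint with 90% power, and accommodate almost 25% attrition". It mentions no change to the difference or the SD.

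Section 4.2 names a two-tailed independent-sample t-test for the primary endpoint, and section 1.2 gives 1:1 allocation. Section 6.3.1 attributes an attrition figure of about 15% to the sample size calculation and uses it to set the number of imputed datasets.

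**The concern.** The recalculation relaxed both alpha and power, and each change lowers the required number. Halving the type II error and roughly halving alpha are large changes, yet the stated size falls only from 98 to 93. That is hard to square with an unchanged difference and SD.

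Footnote 1 uses 93 to support its closing statement about 90% power and almost 25% attrition. If 93 does not come from the inputs that section 6.1 names, a reader cannot reproduce that statement or tell which SD the current 90% refers to. Table 15 also sets 93 beside a total that was built from 98.

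**Working it through.** **Inputs.** Difference 2.27 and pooled SD 4.06 (Table 15); saline SD 4.73 (Table 15); two-sided alpha 0.049 and power 0.90 (section 6.1); original alpha 0.025 and power 0.95 (footnote 1); 1:1 allocation (section 1.2); t-test (section 4.2).

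**Method.** The normal approximation per group is n = 2 × (SD/difference)² × (z for 1 − alpha/2 + z for power)². The exact figure is the smallest n at which the noncentral t gives the required power, with 2n − 2 degrees of freedom and noncentrality difference / (SD × √(2/n)).

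**Step 1: reproduce the original 98.** With 2.27, 4.06, alpha 0.025 and power 0.95:
- Normal: 2 × (4.06/2.27)² × (2.2414 + 1.6449)² = 96.6, so 97.
- Noncentral t: 97.89, so 98.

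The original figure is recovered exactly with Table 15's pooled SD and the t-test.

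**Step 2: the same method at the current settings.** With 2.27, 4.06, alpha 0.049 and power 0.90:
- Normal: 2 × (4.06/2.27)² × (1.9686 + 1.2816)² = 67.6, so 68.
- Noncentral t: 68.57, so 69.

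The SAP states 93. At 2.27 and 4.06, 93 per group gives 96.6% power at alpha 0.049.

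**Step 3: a check that needs neither the difference nor the SD.** Footnote 1's two changes alone scale n by

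[(1.9686 + 1.2816) / (2.2414 + 1.6449)]² = 0.699.

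98 × 0.699 = 68.5, so 69. The SAP's own ratio is 93/98 = 0.949.

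**Step 4: could only one change have been applied?** At 2.27 and 4.06, alpha 0.049 with power kept at 0.95 gives 84.52 (85). Alpha kept at 0.025 with power 0.90 gives 80.68 (81). Neither is 93.

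**Step 5: an input that does return 93.**

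| Difference | SD | Alpha 0.049, power 0.90 | Alpha 0.025, power 0.95 |
|---|---|---|---|
| 2.27 | 4.06 (pooled) | 68.57 → 69 | 97.89 → 98 |
| 2.27 | 4.73 (saline arm) | 92.71 → 93 | 132.41 → 133 |

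The saline SD matches 93 but not 98; the pooled SD matches 98 but not 93. No single SD in the table gives both.

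**Step 6: how 4.06 was pooled.** √[(3.25² + 4.73²)/2] = 4.06, the unweighted form. Weighting by degrees of freedom, √[(29 × 3.25² + 14 × 4.73²)/43] = 3.80, which would need 61 per group, further from 93.

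**Step 7: attrition.**
- 93/0.80 = 116.25, so 117 per group and 234 in total.
- 93/0.75 = 124 per group.
- 98/0.80 = 122.5, so 123 per group and 246 in total.
- 93 evaluable out of 123 is 1 − 93/123 = 24.4% attrition.

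Footnote 1's 117 and 124 are right given 93. Table 15's 246 belongs to 98 at 20%, not to the 93 printed beside it.

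**The case against.** The strongest reply is that nothing practical depends on 93. Enrolment was fixed from 98 per group, which reproduces fully, and 93 is only a later check that 246 is still enough. At the stated inputs that check passes with room to spare: 96.6% power with 93 evaluable per group and 99.2% with 123. Footnote 1's conclusion therefore holds in the safe direction when dropouts are simply subtracted, and section 6.2 allows the sample size only to rise. All of this stands. It limits the point to the stated figure; it does not make 93 the result of 2.27 and 4.06.

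A second reply is that the missing input is visible, since 4.73 is printed in Table 15 and returns 93. The match is good, but the SAP names the pooled SD and never says that the saline SD was used. Treating 4.73 as the actual input is an inference.

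A third reply is that footnote 1 already explains Table 15's 246 and the 20% and 25% allowances as original and revised figures. That is largely fair. The column still pairs 93 with a total it does not produce, and the 15% in section 6.3.1 is not explained anywhere.

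**Conclusion.** The point holds as a correction to a stated planning figure. At two-sided alpha 0.049, 90% power and 1:1 allocation, Table 15's 2.27 and 4.06 give 69 per group, so 93 is about 35% too high for the inputs named (93/69 = 1.35). Either an input changed and footnote 1 does not list it, or 93 is wrong. This rests on the t-test in section 4.2 and on Table 15's values as printed.

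Three stronger readings are tempting, and the documents do not support them.

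- **That the trial is underpowered.** Under the stated inputs the discrepancy is conservative. Even with SD 4.73, 93 evaluable per group gives 90.1%.
- **That the basis of enrolment cannot be traced.** It can: 98 per group at 2.27, 4.06, alpha 0.025 and power 0.95, then 20% dropout, gives 246.
- **That carrying baseline forward for withdrawals related to index-knee OA (section 6.3.1) must shrink the difference in the ITT analysis and use up the margin.** This depends on withdrawal rates by arm, which the documents do not give. With means 7.20 and 4.93, the difference grows once the HA rate exceeds 7.20/4.93 = 1.46 times the APS rate. For example, assumed rates of 10% on APS and 20% on HA give 0.90 × 7.20 − 0.80 × 4.93 = 2.54, above 2.27. With equal rates it would shrink. No general statement is justified.

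**What to change.** Keep 246. In section 6.1, Table 15 and footnote 1, do one of the following:

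- (a) State the SD (or difference) that produced 93, and list that change in footnote 1 beside the changes to alpha and power; or
- (b) Keep 2.27 and 4.06, state 69 per group for 90% power and 96.6% power at 93 evaluable per group, and note that 4.06 is the unweighted pooled SD.

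In either case, correct the last column of Table 15: 93 at 20% attrition is 234 in total, while 246 is 98 at 20%, or 93 evaluable per group at 24.4% attrition. Reconcile the 15% attrition that section 6.3.1 attributes to the sample size calculation with the 20% and 25% in section 6.1.

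The cost is a few sentences and one table cell in the SAP. Enrolment, the primary test and alpha do not change.
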